4.4.5. Process measures (qualitative interviews)

The pilot study seeks to evaluate the acceptability and feasibility of having pharmacists administer methadone therapy under the supervision of OTP physicians to improve safe access to evidence-based treatment. Patient and physician or pharmacist attitudes, assessed in the pilot study, influence and ultimately determine adoption of new treatment modalities (Rieckmann, Daley et al., 2007). The patient, physician or pharmacist, and organizational attitudes are key inputs to adoption of new evidence-based approaches in healthcare settings (Damschroder et al., 2009). In the case of this pilot study, the quality of transfer of the OTP treatment to a pharmacy environment is crucial and will be adopted as a process measure. The Treatment Satisfaction Survey administered during the study to participants, pharmacists, and physicians will inform the link between treatment process and outcomes.

Additionally, at the end of the pilot study, we will conduct a qualitative interview of participating OTP's staff (e.g., physicians/medical staff, nurses, counselors), pharmacists, and study participants at the end of the study about barriers and facilitators of implementing this pilot program of pharmacy-based dispensing of methadone for the OUD maintenance care. The information will be critical to informing the future designs of the pharmacy-based dispensing and supervised methadone consumption program, including its multisite clinical trials. These interviews may be completed in-person at the OTP/pharmacy or remotely via phone or a Duke-approved teleconferencing platform.

4.5. Methadone diversion policy and prevention for diversion risk

4.5.1. OTP programs: Study participants will follow the OTP program's routine methadone diversion policy (Morse Clinic of North Raleigh, NC; Morse Clinic of Zebulon, NC), which requires patients to have active working phone numbers that the medical staff (e.g., nurse) will call when Methasoft randomly selects patients whose dispensed take-home doses have been recalled. All recalled doses must be returned to the program within 24 hours for staff inspection.

✚ For this study, each study participant must have at least one Methadone Call-Back selected at random after the first methadone dispensing at the pharmacy.

4.5.2. Community pharmacy: The pharmacy (Health Park Pharmacy, Raleigh, NC) will adhere to the following procedures to avoid any possible confusion and to reduce the chance of diversion.

- ✚ Prior to participating in this research study, the pharmacy will brief all employees regarding the nature of the study, its purpose, and each participant's role in the study. This will include all new employees hired during the course of this study.
 - ✚ Prior to the start of this research study, the pharmacy will obtain documentation from the participating prescribing practitioners confirming each has been granted an exception by DEA to 21 C.F.R. §§ 1306.07(a) and 1306.04(c), thereby allowing these practitioners to issue prescriptions for methadone to the patients of the study for the purpose of opioid maintenance.
 - ✚ Health Park Pharmacy will consult with their local DEA field office to determine what additional physical and alarm security, if any, will be necessary for participating in this study.
 - ✚ When the pharmacy receives a prescription as part of this study, the dispensing pharmacist will review each prescription to ensure it contains all required information as outlined in 21 C.F.R. § 1306, and will not fill such prescriptions if the required information is lacking. The prescription will include both the prescribing practitioner's DEA registration number and the DEA registration number of the participating OTP.
 - ✚ Pursuant to 21 C.F.R. § 1301.71(a), the dispensing pharmacist will confirm the patient's identity prior to dispensing methadone in response to each such prescription, and will confirm the patient remains part of the research study. The OTP will also notify the participating pharmacies each time a patient is removed from the research study and returned to routine care at the OTP.
 - ✚ Pharmacy staff will direct all patients who present in the pharmacy earlier or later than the scheduled visit date to the OTP for evaluation and medication. The Pharmacy staff will also contact the OTP to inform them of this development.
 - ✚ The pharmacist will provide patient education regarding dose administration and safe storage of methadone.
 - ✚ The pharmacist who dispenses the methadone will review and confirm what is dispensed, and will observe the patient take the first dose prior to the patient's departure from the pharmacy.
 - ✚ Methadone will be dispensed in child-proof bottles that are properly labelled.
 - ✚ The pharmacy will communicate with the participating OTP and make them aware of any concerns they note during the course of this study. Any indication of drug misuse or diversion will prompt the pharmacy to direct the patient to the participating OTP for evaluation and medication.
 - ✚ Pursuant to 21 C.F.R. § 1301.74(c) the pharmacy will notify their local DEA field office within one (1) business day of discovery of any theft or significant loss of methadone for this study.
 - ✚ The practitioners in this research study have been advised that the exception granted to them will end twenty-four (24) months from the date of their letter, or sooner if the research study ends prior to that date.
- 5. Study duration and number of study visits required of research participants.**
Study participation includes the baseline assessment and three monthly follow-up research assessments. As noted above, participants will be asked to complete study specific assessments at baseline and months 1 through 3 following the administration of the first methadone dose at the pharmacy.
- 6. Blinding, including justification for blinding or not blinding the trial, if applicable.**
This is a pilot demonstration study. All participants will be assigned to the same treatment condition.
- 7. Justification of why participants will not receive routine care or will have current therapy stopped.**

The enrolled participants will receive their methadone under the supervision of study pharmacist during the study period. All other aspects of routine care will remain the same. Study participants will attend the pharmacy the same number of times/week as required at the OTP at the time of study enrollment for methadone administration and dispensing of take-home doses. Study participants will continue to receive their usual care at the OTP (e.g., counseling, prescription orders, urine drug screen), and they will return to their OTP at the end of the study. Study participants will also be able to, alternatively, withdraw from participating in the study at any point during the study period.

8. **Justification for inclusion of a placebo or non-treatment group.**

There is no placebo or non-treatment group in this study.

9. **Handling of missed visits and substance use**

Although the study participants will be stable patients, it is possible that they relapse to illicit drug use which may be manifested by missing appointments. It is also the possibility that scheduling conflicts may occur during the study, which will be addressed as described below.

- **If a participant presents to the pharmacy for take-home methadone administration/dispensing earlier or later than their scheduled visit date**, pharmacy staff will contact the prescribing physician (Site PI) before any medication is administered/dispensed to determine the course of action. Participants will be directed to the OTP for evaluation and medication administration/dispensing for that visit. Pharmacy staff will contact the OTP and the site PI to inform them of this development and document the event in the **Methadone Visit Checklist**. Possible outcomes of this evaluation may include:

- (1) return to pharmacy dispensing condition,
- (2) return to routine OTP methadone dispensing, or
- (3) loss of some or all of take-home methadone privileges for up to 6-months.

The outcome of the evaluation will be communicated the pharmacy and research staff as soon as possible.

- **If the participant fails the OTP program's routine methadone take-home recall procedure during the study or any tampering/diversion is suspected**, the participant will be discontinued from the study and returned to the OTP for methadone dosing and adjustment of their take home schedule as determined by the OTP provider.
- **If illicit or non-prescribed opioid use is reported, found on drug testing, or suspected at any time during treatment**, the participant will be contacted to perform at least one random urine drug use test prior to the next scheduled visit and referred to the study physician for an assessment and to determine whether the participant should continue in the study.
- **Any non-prescribed use of benzodiazepines that is detected will prompt analogue measures to those adopted for opioid use**. The abuse of other substances or alcohol will result in early termination from the study and return to the OTP for methadone dosing and possible adjustment of the take home schedule.

Missing monthly research assessment visits and the rule for early study termination

- If the participant misses a scheduled monthly research assessment visit, alternative visits will be scheduled to collect the data.
- Missed visits will be documented using the Missed Visit Form. Remote/virtual interviews by phone or a Duke-approved teleconferencing platform for research may be used to collect study assessments for missed visits.

10. **Participant Discontinuation**

All participants will be followed for the duration of the study (approximately 3 months for pharmacy OUD maintenance) unless they withdraw consent, stop the methadone medication for OUD, die, or the investigator or sponsor decides to discontinue their enrollment for any reason. In addition to what is

described previously (discontinuation based on missed visits and/or illicit substance use), reasons for the investigator or sponsor to terminate a participant from the study may include, but are not limited to: study participation becoming unsafe, the participant becoming a threat to self or others, lack of funding, or early termination of the study for safety reasons. Of note, participants who discontinue methadone for any reason will be discontinued from the study.

- If a participant is discontinued from the study, an Early Termination Visit and End of Medication form should be completed as soon as possible following participant discontinuation to assess the participant's safety.

11. Description of what happens to participants receiving therapy when study ends or if a participant's participation in the study ends prematurely.

Following the end of participation in the study, either at 3-months following the first pharmacy dose or sooner for cause, participants will continue to receive all available routine care, with dispensing of methadone within the Morse Clinic OTP program.

12. Drugs/Substances/Devices

- **The rationale for choosing the drug and dose or for choosing the device to be used:**
The study is investigating the feasibility of administering and dispensing methadone to opioid-dependent patients in a pharmacy setting, and its acceptability to participants, pharmacists and OTP treatment staff.

The study will **not** evaluate a device.

- **Justification and safety information if FDA approved drugs will be administered for non-FDA approved indications or if doses or routes of administration or participant populations are changed:**
Not Applicable.
- **Justification and safety information if non-FDA approved drugs without an IND will be administered:**
Not Applicable.

13. Study Statistics

13.1. Primary outcome variable

- **Treatment adherence:** Adherence to medication is defined as the proportion of participants receiving their scheduled methadone dose administration and methadone dispensed at the pharmacy pickup out of the methadone prescribed. Treatment adherence will also be checked randomly by a methadone dose call-back (at least once during the study period). Failure to attend the random methadone dose call-back visit will be considered as an indicator of non-adherence.

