The operation for the pharmacy administration and dispensing of methadone for OUD treatment will be based on the available treatment guidelines for pharmacy-based medication management and Medication-assisted treatment (MAT) for OUD, including SAMHSA's guidelines to the federal OTP regulations and the guideline for pharmacy-based supervision of methadone consumption from other countries (Adams et al., 2015; Hill, 2014; Ontario Pharmacists Association, 2017; SAMHSA, 2015a, 2015b; SAMHSA, 2018a;). An Operational Care Agreement (OCA) will be used to define the respective roles of the methadone medical provider (supervising care and writing prescriptions) and pharmacist and determine study procedures. The OTP will continue to follow routine care practices and procedures as usual during the study and provide counseling, medical supervision, and urine drug testing. The study pharmacist will administer and dispense methadone according to the OTP provider's prescription.

Participants will be assessed at baseline (following informed consent). Outcome assessments will be conducted at each monthly visit throughout the follow-up phase of the study. Assessments will focus mainly on the feasibility and acceptability of pharmacy-based methadone administration and dispensing in order to inform the development of a future multisite randomized clinical trial. **Primary outcome** will be medication adherence. Measures of adherence will include: (1) adherence to scheduled pharmacy visits for dose administration and take-home pickup and (2) success in methadone call-back (e.g., failed methadone dose call back as an indicator treatment non-adherence). **Secondary outcomes** will include recruitment rate, treatment retention, opioid and other substance use, participant treatment satisfaction, pharmacist and physician treatment satisfaction, and participant safety. Information generated from this pilot study will inform the development of a future randomized controlled trial, which will test the effect of pharmacy-OTP collaborative care model for the management of patients with OUD.

2. Objectives

The overarching goal is to explore the feasibility and acceptability of transferring methadone dose administration and take-home methadone dispensing for OUD treatment for stable patients from OTPs to pharmacies. We will achieve this goal by pursuing the following primary pilot study objectives.

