- a) Calculate the rate of recruitment, defined as the number of participants enrolled in the study out of the number of MMT patients who are potentially eligible and approached for participation. The average monthly rate of participants starting pharmacy-based methadone dispensing for OUD among enrolled participants will also be calculated. The number of potential participants pre-screened and the reasons for pre-screen failure and screen failure will also be evaluated.
- b) Calculate the adherence to methadone treatment defined as (1) the proportion of methadone take-home doses dispensed at the pharmacy out of the total number of take home doses prescribed and (2) the proportion of successful scheduled methadone dose call-back with no signs of methadone diversion.
- c) Examine retention in treatment, as determined by the proportion of participants who remain in treatment at the pharmacy during the 3-month follow-up phase.

- d) Examine the proportion of positive urine drug screens (UDS) over the study duration.
- e) Examine the number of days of self-reported substance use (alcohol intoxication, and other drugs) as collected on Timeline Followback (TLFB) over the study duration (Sobell, 1992; Sobell & Sobell, 2000).
- f) Determine indicators of participant satisfaction with treatment delivery measured using the Treatment Satisfaction Survey (adapted from Harland et al., 2005) obtained at each assessment; proportion of visits in which raters are satisfied (score of 4 on a Likert Scale of 1-5) or very satisfied (score of 5 on a Likert Scale of 1-5).
- g) Determine pharmacist and physician satisfaction with treatment delivery measured using the Treatment Satisfaction Survey at follow-up assessment, and a proportion of physician and pharmacist ratings of satisfied or very satisfied.
- h) Examine participant safety, as measured by: (1) Any fatal or non-fatal substance-related overdose measured by medical examiner record or self-report, respectively; and (2) Any substance-related emergency department (ED) visit or hospitalization, measured by self-report.

3. Background and rationale

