4.4.4. Methadone Treatment Assessments

Methadone Visit Checklist: This form will be completed by the study pharmacists to document all study medication administered and dispensed at each Pharmacy visit, including the daily prescribed dose of methadone and the lot number and expiration date of administered/dispensed medication. This form also will be used to document pharmacist-provided care, such as (1) performing methadone prescription reconciliation, (2) providing patient education (e.g., safe storage, medication side effects); (3) checking and recording the patient's controlled medications prescription status using the NC Controlled Substances Reporting System [CSRS]; (4) monitoring and recording safety related events/concerns and communicating with the OTP medical physician or staff promptly regarding the event/concern; and (5) administering one methadone dose at the pharmacy and dispensing methadone according to the prescription of the OTP physician and applicable federal/state guideline for methadone treatment for opioid use disorder. Communications between the study pharmacist and the OTP medical physician or staff will be documented on the form, such as reasons for changes in methadone doses and/or take-home schedule.

Methadone Call-Back: The OTP medical staff (e.g., nurse) will implement the call back procedure. This form will collect the written results provided from the OTP medical staff to document the outcome of each random methadone call-back visit during the study period (i.e., at least once for every study participant after the first methadone dispensing by study pharmacist(s)), including the amount of used and unused medication returned. Failure to successfully complete call back result in termination from the study and return of the participant to the OTP for further assessment and ongoing treatment. This Methadone Call-Back form will include questions assessing whether a random methadone call-back visit is completed, its date, and the outcome of the call back (e.g., brought back all doses or not). The OTP staff is required to sign and date the form that a call back was done and its results (e.g., brought back all doses or not).

Treatment Satisfaction Survey: Participants, pharmacists and methadone treatment physicians will be asked to rate their overall satisfaction with the quality of the treatment (modified from Harland et al., 2015). Participant

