- ✚ If the participant fails to return to the pharmacy for the random methadone call back visit during the study or any tampering/diversion is suspected, the participant will be discontinued from the study and returned to the OTP for methadone dosing and adjustment of their take home schedule as determined by the OTP provider.
- ✚ If the participant misses two consecutive visits, he/she will be discontinued from study and contacted by pharmacist/research staff to complete the Early Termination Visit and be referred back to the OTP clinic.

15.3. Plan for reporting unanticipated problems or study deviations.

All protocol-defined safety events (medical and/or psychiatric) occurring during the course of the study will be assessed, documented, and reported. Safety events occurring during the course of the clinical trial will be collected, documented, and reported by the PI and/or site PI according to the Manual of Operating Procedures. Appropriately qualified and trained personnel will elicit participant reporting of safety events at each study visit designated to collect safety events (i.e., the first visit following informed consent and at every study visit thereafter).

A study Medical Monitor ([name]) will review or provide consultation for each safety event as necessary. The study Medical Monitor, study PI, and site PI will also make decisions to exclude, refer, or withdraw participants as required. The study staff will be trained to monitor for and report safety events. Individuals who experience a safety event that compromises safe participation in the study will be discontinued from further medication administration and provided referrals for other treatment or to specialized care. Study personnel will request that the participant complete an Early Termination Visit to assure safety and to document end-of-intervention outcomes.

- ✚ Serious adverse events (SAEs) will be reviewed by study Medical Monitor and discussed with PI, Site PI and other investigators, and reported to the Duke IRB based on the current Duke IRB policy:
 - Immediately (within 24 hours) upon learning of an unanticipated study-related death, study personnel will notify the IRB via phone or email by providing a brief summary of the event. Then within 1 week (5 business days), study personnel will send to the Duke IRB a Safety Event submission.

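### The primary adherence outcome is stated in conflicting units, the section 13.1 version cannot be computed as written, and no rule says how doses after discontinuation enter the denominator

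*Combined protocol and SAP*

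**What the plan says.** Adherence is the primary outcome, and it has two parts: supply through the pharmacy, and the random call-back. The supply part is described in three ways.

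- Section 1 (Abstract) and section 15.2 item (4): "adherence to scheduled pharmacy visits for dose administration and take-home pickup". The unit is the visit.
- Section 2, objective b(1): "the proportion of methadone take-home doses dispensed at the pharmacy out of the total number of take home doses prescribed". The unit is the take-home dose. The dose observed at each visit (section 4.3) is left out.
- Section 13.1: "the proportion of participants receiving their scheduled methadone dose administration and methadone dispensed at the pharmacy pickup out of the methadone prescribed". The numerator is people and the denominator is drug.

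For the call-back, objective b(2) requires success without any sign of diversion. Section 13.1 names only failure to attend.

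Pharmacy supply can stop early. Section 4.4.4: "Failure to successfully complete call back result in termination from the study". Section 15.2: "If the participant misses two consecutive visits, he/she will be discontinued from study". Other exits have nothing to do with adherence: pregnancy (section 4.4.2), prisoner status (section 4.4.1), and the section 10 list, which includes "the participant becoming a threat to self or others, lack of funding, or early termination of the study for safety reasons".

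Single visits can also move to the OTP. Under section 4.5.2, pharmacy staff will "direct all patients who present in the pharmacy earlier or later than the scheduled visit date to the OTP", and section 9 says "Participants will be directed to the OTP for evaluation and medication administration/dispensing for that visit".

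Section 13.3 plans descriptive analysis, with GEE models to be considered for repeated measures. It does not say how doses after discontinuation, or doses moved to the OTP, enter the adherence proportion.

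**The concern.** Section 13.1 is the statistical definition of the primary outcome, and an analyst cannot apply it without making a choice that the plan does not make. A dose-level reading needs the numerator changed to doses. A participant-level reading needs the denominator changed to participants and a threshold added.

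The second gap concerns the denominator. Objective b(1) can be computed. Read literally, however, a dose that was never prescribed to the pharmacy, because the participant had already been discontinued, is not in its denominator. Two of the discontinuation triggers are themselves non-adherence, so this reading can favour a high figure when participants leave for that reason.

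The pilot is meant to inform a multisite randomized trial. Its adherence figure should not depend on a reading chosen after the data have been seen.

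**Working it through.** The plan states no adherence target, threshold or expected value, so there is no figure to reproduce. The event counts below are assumptions that show sensitivity. They are not predictions.

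**Inputs from the protocol.** Up to 20 participants (section 4.1). Pick-up weekly or every two weeks, with one observed dose per visit (section 4.3). Take-home supply of 6 to 13 days (section 4.1). About 3 months at the pharmacy.

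**Common assumptions.** 20 starters. 12 weeks stand for 3 months, so each has 84 daily doses: weekly 12 × (1 + 6) = 84, two-weekly 6 × (1 + 13) = 84.

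**Check 1: does the unit matter?** Assume 10 participants on each schedule. One per schedule is discontinued at mid-study, after receiving everything due until then. Three others (two weekly, one two-weekly) each have one visit redirected to the OTP.

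- Planned: 120 + 60 = 180 visits; 720 + 780 = 1500 take-home doses; 1680 doses in all.
- Lost after discontinuation: 6 + 3 = 9 visits; 36 + 39 = 75 take-home doses; 84 doses.
- Redirected: 3 visits; 6 + 6 + 13 = 25 take-home doses; 28 doses.

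| Unit | Planned schedule | Up to discontinuation |
|---|---|---|
| Visits | 168/180 = 93.3% | 168/171 = 98.2% |
| Take-home doses | 1400/1500 = 93.3% | 1400/1425 = 98.2% |
| All doses | 1568/1680 = 93.3% | 1568/1596 = 98.2% |
| Participants with every dose from the pharmacy | 15/20 = 75.0% | 17/20 = 85.0% |

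In the last row the two discontinued participants fail on the planned schedule and pass up to discontinuation. So the contrast of 98.2% with 75.0% combines a change of unit with a change of denominator. Like for like it is 93.3% against 75.0%, or 98.2% against 85.0%.

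The threshold matters as much. With an assumed cut-off of 80%, the redirected participants (11/12 = 91.7% or 5/6 = 83.3%) all pass. The participant figure becomes 18/20 = 90.0% on the planned schedule and 20/20 = 100% up to discontinuation.

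If redirected doses are removed from the denominator, the dose figure up to discontinuation is 1400/1400 = 100%.

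Taken literally, section 13.1 gives 15 participants / 1680 doses = 0.009, which is not a proportion of anything.

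Visits and doses barely differ. One missed two-weekly visit in this mix gives 179/180 = 99.4% of visits and 1666/1680 = 99.2% of doses.

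**Check 2: does the denominator matter?** Assume k participants leave having received 4 weeks of supply (28 doses) and that everyone else receives everything. Received = (20 − k) × 84 + 28k.

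- Planned schedule: received / 1680.
- Exit for a failed call-back: nothing further is prescribed to the pharmacy and no visit has been missed, so prescribed doses give received / received = 100%.
- Exit for two missed visits, read as pharmacy visits, with both prescriptions already written: the denominator gains 2 × 14 = 28 doses per exit (two-weekly) or 2 × 7 = 14 (weekly).

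| k | Planned | Failed call-back, prescribed | Missed visits, two-weekly | Missed visits, weekly |
|---|---|---|---|---|
| 0 | 100% | 100% | 100% | 100% |
| 1 | 1624/1680 = 96.7% | 100% | 1624/1652 = 98.3% | 1624/1638 = 99.1% |
| 2 | 1568/1680 = 93.3% | 100% | 1568/1624 = 96.6% | 1568/1596 = 98.2% |
| 4 | 1456/1680 = 86.7% | 100% | 1456/1568 = 92.9% | 1456/1512 = 96.3% |

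Counting take-home doses only, as objective b(1) does, gives the same proportions. For k = 4, two-weekly, received = 16 × 78 + 4 × 2 × 13 = 1352, so 1352/1456 = 92.9%.

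The gap from the planned schedule for k = 1, 2 and 4 is 3.3, 6.7 and 13.3 points for failed call-backs. For missed visits it is 1.6, 3.2 and 6.2 points (two-weekly) or 2.5, 4.9 and 9.6 points (weekly).

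**The case against.** The strongest reply is that the defect is loose wording in a small descriptive study. Section 13.3 states no hypotheses and section 4.1 makes no power claim, so no test or decision turns on the figure. Objective b(1) is a usable formula. Each visit supplies the observed and take-home doses together, so visit and dose measures nearly coincide. The primary outcome also has a call-back measure: a participant removed for a failed call-back may score 100% on b(1), but b(2) records the failure. Doses already prescribed for missed visits stay in b(1)'s denominator and count against adherence. Exits may also be rare: eligibility requires 12 months without a missed call-back, and section 3.3 cites one US report in which none of 13 pharmacy patients left and another with no failed recalls.

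Most of this stands and limits the point. The conflict between visits and doses has little numerical effect, k = 4 is a stress case, and with no exits the denominator gap disappears. A denominator that keeps every planned dose is not plainly right either. Used alone, it would merge adherence with retention, which objective c covers, and would count pregnancy or loss of funding as non-adherence.

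Two things are not answered. Section 13.1 allows both a dose-level and a participant-level reading, these differ materially, and no threshold is given. And no section says where doses after discontinuation, or doses redirected to the OTP, belong.

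**Conclusion.** The point holds and should be fixed before the data are examined. The primary outcome is stated in conflicting units, and the section 13.1 sentence is not computable as it stands. In the illustration, the choice between doses and participants moves the figure from 98.2% to 75.0%, part of which is the denominator. The denominator alone moves it by 3.3 to 13.3 points for 1 to 4 failed-call-back exits, by 1.6 to 9.6 points for missed-visit exits with prescriptions already written, and not at all without exits. These sizes rest on the assumed 20 starters, 84 doses, week-4 exits and event counts.

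A reader might infer more than the documents support:

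- That the plan adopts a rule removing doses after discontinuation. It states no rule. The omission follows only from reading the word prescribed literally.
- That every exit for non-adherence scores 100%. This holds for a failed call-back with no missed visits, but not for missed visits whose prescriptions were written.
- That short returns or diversion go unrecorded. Sections 4.4.2, 4.4.4 and 15.3 capture them. Only the section 13.1 wording is narrower than objective b(2).
- That the study's conclusions are invalid. No error rate or decision rule changes. What suffers is the interpretation of a feasibility estimate.

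**What to change.** Replace the section 13.1 sentence with one dose-level definition, and use it in sections 1, 2 and 15.2(4). For each participant who starts at the pharmacy, divide the doses received through the pharmacy (observed plus take-home) by the doses scheduled. Summarise as the distribution of participant proportions.

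Report two denominators side by side:

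- (a) all doses scheduled from Visit 2 to Month 3 on the schedule at enrolment;
- (b) doses scheduled up to discontinuation, with missed visits counted.

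Add a table of reasons for discontinuation, so that exits for non-adherence are separated from pregnancy, prisoner status and administrative exits. Give visits redirected to the OTP as a separate count, so that their share of any shortfall is visible. Report call-back success as a separate participant-level proportion, with section 13.1 adopting the objective b(2) criterion, so that a call-back attended but showing signs of diversion is not a success.

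The cost is wording in four sections and a little more analysis. The Methadone Visit Checklist, Methadone Call-Back form, Study Completion form and End of Methadone Medication Form should supply the data. If they hold no reason for discontinuation, one item must be added. The figure on denominator (a) may look less favourable.
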